This conceptualization derives from evidence that biological changes in the circadian system at puberty lead to a shift in sleep timing preferences toward a delayed sleep phase. This effect is compounded by psychosocial changes including less parental control, increased access to stimulating social activities (movies, music, internet, texting, cell phones) and intake of alcohol and substances that contribute to sleep disruption. The social influences are synergistic with biological tendencies toward phase delay and can spiral quickly into a pattern of extremely delayed bedtimes. Yet, school or work usually requires a fixed early wake-up time. These forces converge to constrain the time available for sleep, resulting in high rates of insufficient sleep among youth. Compounding the negative cycle, most attempts to “catch-up” on sleep occur on weekends with an extremely phase-delayed schedule. This is a critical problem because the human circadian system adapts more easily to phase delays; endogenous rhythms are able to re-set quickly to later bed and wake times, but have more difficulty accommodating to phase advances (earlier sleep schedules). The problematic result is that large numbers of youth are struggling with the burdens of eveningness, sleep deprivation and the consequences of repeated circadian shifts. This is of particular concern for rapidly developing teens because adequate sleep is critical for optimal brain development.

This research will advance current knowledge on the role of eveningness as a mechanism contributing to poorer outcomes during adolescence. We aim to reduce eveningness among 10-18 year olds via an innovative intervention; the Transdiagnostic Sleep and Circadian Intervention (TranS-C) which integrates elements from four evidence-based treatments (Cognitive Behavior Therapy for Insomnia, Interpersonal and Social Rhythm Therapy, Chronotherapy, and Motivational Interviewing) derived from basic research on the circadian system. We will randomly allocate adolescents (10-18 year olds) with an evening circadian tendency, and who are ‘at risk’ in at least one of five health domains (emotional, cognitive, behavioral, social, physical), to either: (a) TranS-C or (b) Psychoeducation. Measures will be taken pre-treatment, at the end of treatment, and at 6 and 12 months post-treatment.

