## 5. DATA ANALYSIS

Sample size will be determined via power analysis. Power analyses will be conducted based on the average of Cohen's  $d$  (0.48) across estimations of the effect of treatment on sleep duration (for sleep outcomes) and the five primary health outcomes. Specifically, for sleep outcomes Cohen's  $d$  will be calculated from the pre-post deviation scores across TranS-C and Psychoeducation conditions. For the five health domains we will use: our pilot data for emotional health and behavioral health recent meta-analyses for cognitive health and physical health; and unpublished data from a collaborator's lab for the impact of poor sleep on social interactions. G\*Power 3.1 was used to estimate sample size using Cohen's  $d = 0.48$ , assuming significance of 0.05 and power of at least 80%. Sixty nine participants are needed for each condition. We will recruit 20% more for potential attrition. There will be no interim analyses.

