Data analysis will be conducted in Stata 14 (StataCorp, 2015). All analyses will be adjusted for age and sex, which will be the stratification factors used during randomization. Using intent-to-treat, multilevel modeling with maximum likelihood estimation with the assumption of missing at random will be used to examine continuous outcomes. The fixed component of the model will include stratification factors (age and sex), an indicator for time period (Time=0 pre-treatment, Time=1 post-treatment), an indicator for treatment condition (Treatment=1 TranS-C, Treatment=0 PE), and a Time by Treatment interaction term. The random part of the model will include a subject-specific random intercept and a time and subject-specific error term. The treatment effect of interest will be the interaction, representing the difference in mean change from pre-treatment to post-treatment between TranS-C and PE. The model will also provide estimates of the mean pre-to-post change in the PE condition (coefficient of Time) and in the TranS-C condition (coefficient of Time plus interaction coefficient), and the significance of these changes will also be reported regardless of the significance of the interaction because PE may be an active control and can be beneficial. Using Hochberg's procedure, the outcomes will be considered two subfamilies of analyses. The error rate in each subfamily will be controlled under 0.025 using the Hochberg's step-up procedure, so that the overall family-wise error rate will not exceed 0.05.

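### The promised 6- and 12-month follow-up has no specified analysis; the pre-to-post contrast is valid but generally less precise than a baseline-adjusted one where the baseline precedes randomisation

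*Combined protocol and SAP*

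**What the plan says.** **Time points.** Section 1 (Purpose) states: "Measures will be taken pre-treatment, at the end of treatment, and at 6 and 12 months post-treatment". It closes with an aim that covers both short-term and long-term improvement. Section 4 sets payments to participants and parents for a 6-month and a 12-month follow-up. Section 2.1, by contrast, names only baseline and end of treatment. Section 3 opens with before-and-after administration as the default, and none of its instruments is then given a follow-up administration.

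**Model.** Section 5 holds the only analysis text. The fixed part has age and sex, "an indicator for time period (Time=0 pre-treatment, Time=1 post-treatment), an indicator for treatment condition (Treatment=1 TranS-C, Treatment=0 PE") and the product of the two indicators. For the random part: "The random part of the model will include a subject-specific random intercept and a time and subject-specific error term". The target is stated once: "The treatment effect of interest will be the interaction, representing the difference in mean change from pre-treatment to post-treatment between TranS-C and PE". Within-arm changes are promised as well: "the significance of these changes will also be reported regardless of the significance of the interaction". Outcomes form two subfamilies, and "The error rate in each subfamily will be controlled under 0.025 using the Hochberg's step-up procedure".

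**Sample size.** For the sleep outcomes, Cohen's d "will be calculated from the pre-post deviation scores across TranS-C and Psychoeducation conditions". The averaged d of 0.48 leads to 69 per arm, and then: "We will recruit 20% more for potential attrition".

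**Order of events (Section 4).** The in-person assessment with questionnaires comes first, then the overnight DLMO, then randomisation. A further diary week with EMA calls follows randomisation and supplies the outcome baseline for those measures. Treatment starts a week later.

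**The concern.** Two separate matters arise from the same model.

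1. A two-level time indicator cannot hold four visits. If the follow-up visits take place, then under the plan as written the choice of outcome, contrast, model and error control for the long-term claim stays open until the data can be seen. Section 5 otherwise controls the family-wise error rate at 0.05, but does not say whether follow-up tests fall inside that control.

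2. The model keeps a free Treatment term and adjusts only for age and sex. The baseline value of the outcome is therefore subtracted with coefficient 1 rather than conditioned on. Where that baseline was measured before randomisation, the arms share a baseline mean by design, and the model does not use this. What is at stake is precision, not bias.

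**Working it through.** **Part 1: the passages side by side**

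| Place | Time points |
|---|---|
| Section 1 | pre, post, 6 months, 12 months; long-term aim |
| Section 4, payments | pre, post, 6 months, 12 months |
| Section 2.1 | baseline, end of treatment |
| Section 3, opening | before and after, unless specified |
| Section 3.3.2, DLMO | one night before and one after treatment |
| Section 3.4.2, EMA | one week pre, one week post, 36 calls in all |
| Section 5, model | Time = 0 or 1 |

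The EMA total leaves no room for follow-up: 2 weeks × (5 weekdays × 2 + 2 weekend days × 4) = 2 × 18 = 36. Two of the four promised time points are in no model.

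**Part 2: precision**

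*The plan's own figure.* For d = 0.48, two-sided alpha 0.05 (sidedness assumed) and 80% power, the normal approximation gives 2 × (1.96 + 0.84)² / 0.48² ≈ 68.1, hence 69 per arm. This reproduces. The noncentral t gives power 0.799 at 69.

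*Formulas.* Let ρ be the pre-post correlation and k = SD(pre)/SD(post). With complete data the planned interaction equals the difference in mean change. In one simulated data set, the mixed model and the raw difference both gave 0.3696. In units of the post variance:
- change contrast: 1 + k² − 2ρk, which is 2(1−ρ) at k = 1
- baseline-adjusted contrast: 1 − ρ²
- ratio at k = 1: (1−ρ²) / [2(1−ρ)] = (1+ρ)/2
- no gain when k = ρ, where the baseline slope is 1

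*Results.* ρ is not in the documents; 0.3, 0.5 and 0.7 are assumed.

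| Setting | ρ = 0.3 | ρ = 0.5 | ρ = 0.7 |
|---|---|---|---|
| Equal SDs, complete data | 0.65 | 0.75 | 0.85 |
| 83 with pre, 69 with post, per arm | 0.69 | 0.78 | 0.87 |
| k = 0.8 | 0.78 | 0.89 | 0.98 |
| CMEP (unselected ρ) | 0.885 | 0.925 | 0.959 |

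- Attrition row: 69 × 1.2 = 82.8, taken as 83. Ratio = [(1−ρ²)/m] / [(1−ρ²)/m + (1−ρ)²/n], with n = 83 and m = 69. At ρ = 0.5: 0.01087 / (0.01087 + 0.00301) = 0.78.
- CMEP row: entry requires the lowest quartile (Section 2.2). If scores are normal before selection, the baseline SD falls to 0.49 of its unselected value, a variance of 0.242. Ratio = (1−ρ²) / [(1−ρ²) + 0.242(1−ρ)²]. At ρ = 0.5: 0.75 / (0.75 + 0.0604) = 0.925.

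Over 4,000 simulated trials per setting, both contrasts averaged within 0.003 of the true 0.48. At ρ = 0.5 the empirical standard errors were 0.173 (change) and 0.152 (adjusted). With the baseline cut to the lowest quartile, the simulated ratios were 0.90, 0.93 and 0.96.

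*CMEP power at 69 per arm, d = 0.48 in change-score units.* At alpha 0.05, power rises from 0.799 to 0.845, 0.829 and 0.816. At the subfamily level of 0.025, it rises from 0.709 to 0.767, 0.746 and 0.729.

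**The case against.** **On follow-up.** The document may be meant to cover the post-treatment analysis only, and Sections 2.1 and 3 can be read that way. Section 3 allows for exceptions, so it does not by itself contradict Section 1. The major hypothesis names no time point, and Section 5 does test it at post-treatment. Figure 1 is not shown and may list follow-up measures. All of this stands. But no visible text limits the scope or points to a separate follow-up plan, and a flow diagram would not supply a contrast, a model or a multiplicity rule. A reader might infer that the long-term results will be reported selectively. The documents show only that the choice is left open.

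**On precision.** The interaction is a coherent target, and the sleep effect size was built from pre-post deviation scores, which fits it. This stands: part 2 is an improvement, not the correction of an error. Three stronger readings are tempting and fail.
- *The planned contrast is biased.* It is not. Both contrasts estimate the same effect when the baseline precedes randomisation.
- *All primary outcomes would gain the power implied by 0.65 to 0.85.* The outcome baseline for total sleep time and bedtime follows randomisation, so a common baseline mean is not assured. For CMEP the gain is small. Among primary outcomes the range could apply only to the self-report health composites. For these the documents give neither ρ, nor the SD ratio, nor the scale of d, and the at-risk entry rule may shrink the gain further.
- *The diary week before the overnight stay could serve as covariate for total sleep time and bedtime.* With equal SDs the variance ratio is (1 − a²) / [2(1 − b)], where a and b are the correlations of the earlier and the later pre-treatment week with the post week. Assumed pairs (a, b) of (0.6, 0.7), (0.5, 0.7) and (0.7, 0.8) give 1.07, 1.25 and 1.28, a loss each time. It would also not directly give the within-arm changes that Section 5 promises.

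**Conclusion.** Part 1 holds, with high confidence, on the visible text: the 6- and 12-month visits are promised and paid for, and no contrast is specified for them. The primary pre-to-post test is unaffected. This is the part to act on first.

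Part 2 holds as an efficiency point only. For CMEP, the self-report questionnaires, CBCL and DLMO, baseline adjustment generally lowers the variance. The ratio is 0.65 to 0.85 for assumed ρ of 0.3 to 0.7 with equal SDs and complete data, and closer to 1 with attrition or a restricted baseline. For CMEP it is about 0.88 to 0.96, so power at alpha 0.05 moves from 80% to about 82–85%. These sizes rest on an assumed ρ, on d = 0.48 being in change-score units, and, for CMEP, on normality before selection. Section 4 does not name the CBCL, so placing it before randomisation assumes that it is among the questionnaires of the in-person assessment. For total sleep time, bedtime and EMA, the planned contrast should stay. Its validity there also assumes that the week between randomisation and treatment was not affected by allocation.

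**What to change.** 1. **Follow-up.** Reconcile Sections 1, 2.1, 3, 4 and 5. Before any follow-up data are examined:
   - name the outcomes collected at 6 and 12 months; EMA is excluded by its call total, and whether DLMO is repeated needs confirming
   - for those outcomes, code Time as categorical, with a TranS-C versus PE contrast at each later visit
   - keep the post-treatment contrast primary, and declare the 6- and 12-month contrasts secondary and outside the two Hochberg subfamilies.

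   Keeping them outside leaves primary power unchanged. Assuming subfamilies of 3 and 5 primary outcomes (sizes not stated), bringing two more visits inside would lower the strictest step from 0.025/3 = 0.0083 to 0.025/9 = 0.0028, and from 0.025/5 = 0.005 to 0.025/15 = 0.0017. Power at that step would fall from 56% to 41% and from 49% to 35%. The price of keeping them outside is that long-term findings carry no family-wise control and must be described so.

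2. **Precision.** For CMEP, the self-report questionnaires, CBCL and DLMO, fit a longitudinal maximum-likelihood model with age and sex, a common pre-treatment mean (no Treatment main effect) and an unstructured covariance across visits. The unstructured form matters because a random intercept alone forces equal variances before and after treatment, which a baseline restricted by eligibility need not satisfy. The model keeps the missing-at-random assumption and still yields the within-arm changes. Keep the planned change contrast for total sleep time, bedtime and EMA.

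The cost is SAP wording and a little more analysis. Part 2 needs no new data. Part 1 needs confirmation of what is collected at the two follow-up visits.

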## 2. METHOD

### 2.1. Study Design

Based in a university clinic, youth will be randomly assigned, stratified by sex and age (10-14, 15-18), in a 1:1 parallel group design, to receive either TranS-C or PE. Sibling pairs will be randomized to the same condition.

Assessors will be blind to treatment allocation. Sequentially numbered, opaque, sealed envelopes will be generated using a computer-generated random number list. A project coordinator will conduct randomization after all eligibility assessments are completed. Assessments will be conducted at baseline and at the end of treatment. The Committee for the Protection of Human Subjects approved the study.

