#### **3.2. Sleep Outcomes**

##### **3.2.1 Sleep Diary.**

An a priori decision was made to investigate weeknight average total sleep time (TST) and bedtime (BT) average as primary outcomes to best capture the sleep problems of interest. Secondary outcomes will be the discrepancy between weeknight and weekends for TST, BT, and waketime (WUP). Trained research assistants will phone the participants each morning to collect their sleep diary. In scheduling the call, the participants will specifically be told to not use the call as an alarm clock and to select a time as close as possible to rise time but after they are already out of bed. The training of the research assistants will specifically include not engaging in conversation other than collecting the sleep diary data. (See Table 2 for calculations of sleep diary variables).

Other secondary outcomes will be *Sleepiness Scale*, *Pittsburgh Sleep Quality Index (PSQI)* and *CBCL Sleep Composite (parent report)*.

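### The fixed 0.025/0.025 split between the two subfamilies is valid, but it is uniformly less powerful than a split that passes alpha on once one subfamily is fully rejected

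*Combined protocol and SAP*

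**What the plan says.** The paragraph on the model and multiplicity in section 5 (Data Analysis) says that "the outcomes will be considered two subfamilies of analyses". It continues: "The error rate in each subfamily will be controlled under 0.025 using the Hochberg's step-up procedure". The stated aim is to hold the error across both subfamilies together to 0.05. It does not say which outcomes belong to which subfamily, or what happens to one subfamily's 0.025 when all its hypotheses are rejected.

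The primary outcomes are named elsewhere. Section 3.2.1 gives "weeknight average total sleep time (TST) and bedtime (BT) average as primary outcomes", section 3.3.1 adds the CMEP, and section 3.4.1 marks the youth self-report composite risk score as primary. Section 3.4 builds composites by domain, and section 5 speaks of five primary health outcomes, but the text does not settle whether five domain scores or one overall score will be tested.

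The sample size, also in section 5, assumes d = 0.48, significance 0.05 and at least 80% power: "Sixty nine participants are needed for each condition".

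**The concern.** As written, each subfamily is tested at 0.025 whatever happens in the other. If TranS-C moved every outcome in one subfamily, the other would still be tested at half the error rate the plan allows overall, although a false positive could by then come only from that other subfamily or would already have been made. The unused half buys no extra protection beyond the stated 0.05. What is at stake is power for outcomes with p-values that Hochberg would reject at 0.05 but not at 0.025. The trial has little power to spare, because its sample size was computed at 0.05.

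**Working it through.** **1. The plan's own figures.** Family-wise bound: 0.025 + 0.025 = 0.05, as stated. Sample size, two-sided normal approximation, 1:1 allocation:

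n per arm = 2(z₁₋α/₂ + z₀.₈)² / d² = 2(1.960 + 0.842)² / 0.48² = 68.13, rounded up to 69. This reproduces the plan. Sidedness is not stated; a one-sided test would give 54.

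**2. Power of a single test with 69 per arm.** Power = Φ(d√(n/2) − z₁₋α/₂), with d√(n/2) = 0.48 × √34.5 = 2.819.
- α = 0.05: Φ(2.819 − 1.960) = 0.805
- α = 0.025: Φ(2.819 − 2.241) = 0.718

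For a single test at d = 0.48, recycling can therefore add at most 0.805 − 0.718, about 8.6 points, and only if full rejection of the other subfamily is certain. For 80% power at 0.025, n = 2(2.241 + 0.842)² / 0.48² = 82.5, or 83 per arm.

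**3. Why the error bound is unchanged.** Consider the rule: if all hypotheses in one subfamily are rejected at 0.025, test the other by Hochberg at 0.05.
- True nulls in both subfamilies: passing alpha on requires rejecting a whole subfamily that contains a true null, so an error has already occurred at the 0.025 stage. The chance of any error stays at or below 0.025 + 0.025 = 0.05.
- True nulls in one subfamily only: it is tested at 0.05 at most, so the error is at most 0.05.
- No true nulls: no error is possible.

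This needs only the dependence condition that Hochberg's procedure already needs. Hochberg at 0.05 rejects everything that Hochberg at 0.025 rejects, so no rejection is lost.

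**4. Size of the gain.** Simulation of correlated z statistics, 200,000 replicates per scenario, 69 per arm. Subfamily membership, the correlation and every effect other than 0.48 are assumptions. The sleep/circadian subfamily is TST, bedtime and CMEP unless stated. Average power per outcome at correlation 0.3:

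| Assumed scenario | Sleep subfamily fully rejected | Health: fixed split → recycling |
|---|---|---|
| 3 sleep + 5 health, all d = 0.48 | 44% | 61% → 65% |
| 3 sleep + 1 health composite, all d = 0.48 | 44% | 72% → 75% |
| 3 sleep at 0.6, 5 health at 0.35 | 76% | 28% → 36% |
| Same, but one sleep outcome at 0.2 | 13% | 27.6% → 29.3% |
| Same, but one sleep outcome at 0 | rarely | gain of 0.2 points or less |
| 10 sleep + 5 health, all d = 0.48 | seldom | 61.4% → 62.3% |

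The sleep/circadian outcomes gain too. With all d = 0.48, their average power rises by about 2 points against five health domains (66% to 68%). Against a single composite it rises by 6 to 8 points (66% to 73% at correlation 0.3), because one composite is fully rejected more often than five domains are.

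Across the correlations examined, the health gain was about 8 to 10 points in the 0.6/0.35 case with five domains, and 0.4 to 1.2 points with ten sleep outcomes.

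**5. Error check.** With three very strong sleep effects and five null health outcomes, the simulated family-wise error under recycling was 0.049, 0.046 to 0.047 and 0.039 to 0.040 at correlations 0, 0.3 and 0.6. With a single null composite it is 0.05 by construction.

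**The case against.** The strongest reply is that nothing here is wrong. A fixed split is standard, pre-specified and conservative, and it delivers exactly the error rate it promises. That stands: a reader might infer that the split is a mistake or fails to control error, and neither is so. The absence of recycling is also read from silence, since section 5 does not rule it out.

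A second reply is that the fixed split keeps each subfamily's conclusion independent of the other's, whereas under recycling some claims would depend on full success elsewhere. This is true but is not a real trade-off. The dependence can only add rejections, and every conclusion available under the planned rule survives.

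A third reply is that the gain is conditional and the subfamilies are assumed. This stands and limits the claim. Section 5 does not say that the split is sleep against health; primary against secondary is equally possible. If a single outcome in a subfamily misses significance, nothing is passed on.

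A reader might also infer that the health outcomes are where the trial has least power. The documents do not support this. They give one average effect, 0.48, and no separate effects for sleep and health. With a single health composite at 0.48, health has more power (72%) than the average sleep/circadian outcome (66%).

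**Conclusion.** The point holds as an efficiency improvement, not as an error. The planned rule controls family-wise error at 0.05 but never rejects more, and sometimes rejects less, than a rule that recycles alpha after full rejection of one subfamily.

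At the protocol's d = 0.48 with three sleep/circadian outcomes, the gain is about 4 points per health domain if five domains are tested, or about 3 points for a single composite. Gains of 8 to 10 points for five health domains need the assumed effects of 0.6 on sleep and 0.35 on health, which are not in the documents, and should not be read as the expected benefit. The gain is near zero if one sleep outcome is weak or null, and about 1 point or less for health if the sleep subfamily is large.

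Nor should recycling be read as a cure for the power calculation. The 80% was computed at 0.05, while a lone test at 0.025 has about 72%. In every scenario with all d = 0.48, average power stayed below 80% even with recycling.

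**What to change.** In section 5, before unblinding:
- List the outcomes in each subfamily, stating whether the self-report health outcome is five domain scores or one overall score, and whether secondary outcomes are included. Neither Hochberg's procedure nor a recycling rule can be applied unambiguously without this list.
- Add one sentence, applying in both directions: *If all hypotheses in one subfamily are rejected at 0.025, the other subfamily is tested by Hochberg at 0.05.*

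The cost is the list, one sentence and a slightly longer description of the testing rule. No participants or data are added, the error bound is unchanged and no rejection is lost. The mismatch between sizing at 0.05 and testing at 0.025 or stricter needs separate attention.
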